3. STUDY DESIGN

This study is a pilot study in a total of 12 hematologic patients with prolonged neutropenia and fever, positive signs for IFI on the HR-CT with or without a positive galactomannan test, therefore having a probable (N=6) or possible (N=6) IFI by definition. Within 48 hours of the HR-CT scan these patients will undergo an additional FDG-PET-CT scan (low dose CT) on the mCT (Siemens) camera in the Department of Nuclear Medicine and Molecular Imaging. The FDG-PET-CT will be evaluated qualitatively and quantitatively by calculation of the maximal Standardized Uptake Value (SUVmax).

4. STUDY POPULATION

4.1 Population

Twelve patients with prolonged neutropenia and fever, positive signs for IFI on the HR-CT and a positive (N=6) or negative (N=6) galactomannan-test, therefore having a probable or possible IFI, will be recruited from the Department of Internal Medicine, Division of Haematology. Because these patients are routinely seen in this Department we expect no problem with recruiting these patients.

4.2 Inclusion criteria

Adult patients (age > 18 years) with a hematologic disease who probably or possibly have an IFI. That means:

- Prolonged (or expected prolonged) neutropenia (leukocyte count < $1,0 \times 10^9$ or granulocyte count < $0,5 \times 10^9$, or leukocyte count < $1,5 \times 10^9$ or granulocyte count < $1,0 \times 10^9$ and decreasing due to chemotherapy), and
- Axillary temperature $\geq 38,5^\circ\text{C}$, not reacting on treatment with wide-spectrum antibacterial drugs for 72 hours, and
- A positive HR-CT scan, suspect for an IFI and
 - A positive galactomannan-test in serum or fluid acquired by BAL, or positive in both materials (N=6)
 - A negative galactomannan-test GM in both serum and BAL fluid (N=6)

4.3 Exclusion criteria

- Patients with age < 18 years
- Female patients who are pregnant
- Patients with claustrophobia or other reasons that make the scanning impossible, such as unable to lie still, need of oxygen, and so on.
- Patients who are hemodynamically instable
- (Pre)terminal patients for which the investigation is too burdensome
- Patients who may clinically not be able to undergo the study
- Patients without prolonged or expected prolonged immunocompromised condition (less than 14 days)
- Patients without positive signs of IFI on HR-CT

4.4 Sample size calculation

This study is a pilot study in twelve hematologic patients who have a probable or possible IFI. Because most of these patients will actually have an IFI, we think these are enough patients to study the added value of FDG-PET-CT in this group of patients to conclude if larger patient studies are wanted.

5. TREATMENT OF SUBJECTS

This chapter is not applicable in this study.

5.1 Investigational product/treatment

This is not applicable in this study.

5.2 Use of co-intervention (if applicable)

This is not applicable in this study.

5.3 Escape medication (if applicable)

This is not applicable in this study.

6. INVESTIGATIONAL MEDICINAL PRODUCT

The Investigational Medical Product Dossier (IMPD) of the used PET tracer ^{18}F -FDG can be read in the attached document.

7. METHODS

7.1 Study parameters/endpoints

7.1.1 Main study parameter/endpoint

This is a pilot study. After 12 patients the study will be ended and evaluated.

7.1.2 Secondary study parameters/endpoints (if applicable)

This is not applicable in this study.

7.1.3 Other study parameters (if applicable)

This is not applicable in this study.

7.2 Randomisation, blinding and treatment allocation

This is not applicable in this study.

7.3 Study procedures

When the (conventional) diagnostic tools are performed and a patient probably or possibly has an invasive fungal infection, FDG-PET-CT (low dose CT) scan will be planned as soon as possible, but within 48 hours of the HR-CT scan on the mCT camera (Siemens).

When the (conventional) diagnostic tools are suspicious for an IFI antifungal treatment will be started, independent of the FDG-PET-CT results. Treatment will be continued conform normal treatment procedures, i.e. treatment regime will not depend on the results of the FDG-PET-CT.

Patient recruitment:

Informed consent will be obtained by [name] or [name] from the Department of Internal Medicine, Division of Hematology. When the patient decides to participate he/she will be asked to sign the informed consent form. The normal diagnostic and therapy protocols will not be changed; other imaging studies will not be delayed. Patients can contact an independent doctor (Dr. [name]) in case they feel the need to receive information from a doctor who is not involved in the study.

Preparation and labelling of [¹⁸F]-FDG:

¹⁸F-FDG will be prepared according to the standard protocol at the department of Nuclear Medicine and Molecular Imaging as is described in the IMPD.

[¹⁸F]-FDG-PET-CT protocol:

A routine whole body PET (that means from head till halfway the upper legs) will be performed 60 minutes after the intravenous injection of 3-5 MBq per kilogram [¹⁸F]-FDG conform normal administrated activity in patients. A low dose CT will be

performed simultaneously for attenuation correction and for anatomic correlation with the PET images. The total scanning time will be around 25 minutes.

Evaluation of the FDG-PET-CT scan:

The FDG-PET-CT will be evaluated qualitatively and quantitatively by an experienced nuclear medicine physician, with special attention to finding lesions outside the thorax, the extension of the lesions found compared to the HR-CT lesions and to the intensity of the uptake of FDG by calculating the SUVmax. These quantitative results will be compared to the results of the galactomannan-tests.

Radiation dose considerations:

Use of positron emitting radionuclides means exposure to ionizing radiation. Because of the potential hazard of radiation, guidelines for the exposure of healthy volunteers and patients are specified in "Besluit Stralingsbescherming (BS 2000), artikel 60, Staatsblad 2001, 397", according to the guidelines of the International Commission on Radiological Protection.

The radiation exposure of one FDG-PET-CT (low dose CT) is approximately 9.1 mSv (7.6 mSv for FDG-PET and 1.5 mSv for low dose CT). This complies with category IIb, IRCP 62.

The radiation dose calculation is approved by our local clinical physicist dr. [name].

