9. STATISTICAL ANALYSIS

Statistical analysis is not necessary in this pilot study. The lesions found on the FDG-PET-CT will be described in the report and compared to other diagnostic techniques. The FDG-PET-CT scan will be evaluated qualitatively (by visual evaluation of the uptake) and quantitatively (by calculating the SUVmax). The calculated SUVmax will be compared to the results of the galactomannan-tests. The aim of this study is to see if FDG-PET-CT is able to localize the IFI and if pathognomic signs for IFIs can be found.

We expect positive signs on the FDG-PET scan in all patients with probable fungal infections. Of the six patients with possible infections we expect at least 2 or 3 to have positive signs on FDG-PET scan. If we can find additional information (positive lymph nodes, lesions in other part of the body) we can not predict.

When there is added value of the FDG-PET-CT we will arrange a larger patient study for which statistical analysis is necessary. Power calculation is not applicable in this study because the aim of this study is to get data to plan a larger clinical study with the appropriate power calculation. These data will serve to calculate the power analysis for a subsequent clinical study.

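### Nothing keeps the GM result or HR-CT images from the single PET reader, so the PET findings compared with them are open to test-review bias

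*Protocol*

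**What the plan says.** All of this is in the Protocol; no SAP is at hand.

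- **Blinding.** The section headed "7.2 Randomisation, blinding and treatment allocation" consists of one sentence: "This is not applicable in this study".
- **Order of tests.** Section 7.3 places PET after classification: "When the (conventional) diagnostic tools are performed and a patient probably or possibly has an invasive fungal infection, FDG-PET-CT (low dose CT) scan will be" (the sentence then schedules it within 48 hours of the HR-CT). Section 4.2 makes the GM result part of eligibility, so the group label exists when the patient enters.
- **Reader and task.** Section 7.3 names one reader: "The FDG-PET-CT will be evaluated qualitatively and quantitatively by an experienced nuclear medicine physician, with special attention to finding lesions outside the thorax". The sentence goes on to "the extension of the lesions found compared to the HR-CT lesions and to the intensity of the uptake of FDG by calculating the SUVmax".
- **Groups.** Section 3 describes patients as "therefore having a probable (N=6) or possible (N=6) IFI by definition". Section 4.3 excludes "Patients without positive signs of IFI on HR-CT", so all 12 are HR-CT positive.
- **Comparison.** Section 9 states: "The lesions found on the FDG-PET-CT will be described in the report and compared to other diagnostic techniques". The qualitative read is visual, with no criterion for a positive scan, and SUVmax is set against GM. Section 9 also gives the expected result by group: PET positive in every probable case, and in two or three or more of the six possible cases.
- **Use.** Section 9 says that the data will feed the power calculation of a later, larger study.

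**The concern.** The primary objective is the value that FDG-PET-CT adds to HR-CT and GM. That comparison is informative only if the PET result was reached without knowledge of the other two. Randomisation and allocation do not arise in a single-group study, but masking of the reader does, because the comparison depends on one person's visual judgement.

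Three features combine here: a subjective call without a stated criterion, a comparator result that already exists, and a published expectation by GM group. Together they create the conditions for test-review bias, in which equivocal scans are settled in line with what the reader already knows. At stake are the description of PET findings by GM group, the count of lesions seen only on PET, the relation of SUVmax to GM, and the planning figures taken into the next study. Masking cannot be restored once a scan has been read openly.

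**Working it through.** There is no sample-size or power figure to reproduce: Section 4.4 sets 12 by judgement and Section 9 declares a power calculation not applicable. The check is therefore a comparison of sections, followed by arithmetic for scale.

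**1. Is the reader shielded from HR-CT?** No. Section 7.3 makes comparison with the HR-CT lesions part of the read, and no PET read without HR-CT is recorded first.

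**2. Is the reader shielded from GM or the group label?** Nothing provides for it. Section 7.2 waives blinding. Section 10.2 has Haematology recruit and Nuclear Medicine schedule the scan, but does not say what information travels with the request. Section 11.1 limits access to patient data to the project leader and principal investigators, without saying whether the reader is one of them. The documents neither state nor prevent exposure.

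**3. Which results are exposed?** The visual call is most exposed. SUVmax is a measured value and less exposed, but someone chooses which lesion to measure. Section 2 also relates mean SUV times area to GM, which depends on which lesions are included and how they are outlined.

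**4. Scale with six per group.**
- One changed call moves a group rate by 1/6 = 17 points.
- The lowest pattern that meets Section 9's expectation is 6/6 (95% exact interval 54–100%) against 2/6 (4–78%) or 3/6 (12–88%), a gap of 67 or 50 points.
- If masked reads would give 5/6 and 4/6 (gap 17 points), one upward call in the GM-positive group gives 6/6 and 4/6 (gap 33 points). That already meets the expectation, because the figure for the GM-negative group is a minimum.
- A downward call in the GM-negative group as well gives 6/6 and 3/6 (gap 50 points).

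**5. Illustration under assumptions that are not in the documents.** Let the true PET-positive rate *p* be the same in both groups, from 0.5 to 0.8. Let an unmasked reader move a fraction *q* of discordant calls toward the GM result.

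(a) Shift in the GM-positive group only. The rate becomes p + (1 − p)q, so the bias in the gap is (1 − p)q.
- q = 0.2: 0.5 × 0.2 = 10 points at p = 0.5; 0.2 × 0.2 = 4 points at p = 0.8.
- q = 0.3: 15 and 6 points.
- The chance of 6/6 is [p + (1 − p)q]^6. From q = 0 to q = 0.3 it rises from 0.5^6 = 1.6% to 0.65^6 = 7.5% at p = 0.5, and from 0.8^6 = 26% to 0.86^6 = 40% at p = 0.8.

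(b) Shift in both groups. The GM-negative rate becomes p(1 − q), so the bias in the gap is p + (1 − p)q − p(1 − q) = q, that is 20 or 30 points for q = 0.2 or 0.3. The chance of 6/6 together with at most 3/6 is as follows.

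| q | range over p = 0.5 to 0.8 |
|---|---|
| 0 | 1.0–3.0% |
| 0.2 | 3.8–13.1% |
| 0.3 | 6.7–21.8% |

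Case (b) assumes a downward shift in the GM-negative group, which the documents do not establish (see the objection).

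**The case against.** The case on the other side is substantial, and several parts of it stand.

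- **The reader is not documented as knowing GM.** A reader of Section 7.2 might infer that GM is handed over. The text does not say so: the entry is one template line covering three topics, and recruitment and scanning lie with different departments. This stands, and the point is limited to a risk left open.
- **The instruction to look outside the thorax is not a source of agreement with HR-CT.** It might be taken as steering PET toward the comparator. Section 2 makes extra-thoracic lesions a study question, and an HR-CT of the thorax has no finding there to copy. This stands.
- **Side-by-side reading is needed.** The questions in Section 2 on lesion types, halo and extension require both images, and HR-CT positivity is an entry criterion that cannot be masked. This stands, and it is why the order of reading should change and HR-CT should remain in the second step. The number, site and type of HR-CT lesions can still be withheld at first.
- **The stated comparison with GM is SUVmax.** Visual positivity by GM group appears only as an expectation. This stands and lowers the weight of any arithmetic on visual calls.
- **The direction of bias in the GM-negative group is unclear.** It is tempting to argue that three or four reads settled in line with GM would manufacture the predicted pattern from 4/6 in both groups. Section 9 gives a minimum for that group, which 4/6 already satisfies. Section 4.4 expects most patients to have an IFI, so a low rate there is not plainly the hoped-for result.
- **PET misses may yet be reported.** Section 9 starts its description from lesions seen on PET, from which one might infer that HR-CT lesions without uptake are left out. It does not exclude them, and Sections 2 and 7.3 also start from HR-CT lesions.

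The pilot label answers less than it seems to, since Section 9 passes these data on to the design of the next study.

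**Conclusion.** The point holds as a gap in the reading procedure. Dependence of the read on HR-CT is built into Section 7.3. Dependence on GM is possible and unprevented. The affected results are the patient-level visual call, the lesion counts and, less strongly, SUVmax.

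Its size cannot be derived from the protocol, which does not give the number of equivocal scans. What is certain is that each changed call moves a group rate by 17 points. The ranges for *q* and *p* above are illustrations and rest on assumed values.

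No formal test is planned, so no error rate is affected. Treatment does not depend on PET (Section 7.3), so no patient's care is affected either. The loss is in the credibility of any added value and in the planning data. For a descriptive study of 12 patients this is a should-fix.

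**What to change.** Replace the entry in Section 7.2 and the reading paragraph in Section 7.3 with a two-step read by the same physician.

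1. **First read.** PET with its low-dose CT, without the GM result, the probable/possible label or the HR-CT images. The reader will know from eligibility that HR-CT is positive. Record and lock the patient-level call, the lesion list and the SUV values.
2. **Second read.** Open the HR-CT and its routine report for the extension, halo and lesion-matching questions. List each lesion as seen on both, on PET only or on HR-CT only, and lock the list.
3. **Release of GM.** Disclose GM and the group label only after both reads are locked. State in Section 9 that first-read calls and SUV values are the ones compared with GM.

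The cost is slightly more reading time per scan and a short form, plus care that the scan request does not carry the GM result or label. No second reader, extra scan or additional HR-CT reading is needed. The change has to be in place before the scans are read.

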7.4 Withdrawal of individual subjects

Subjects can leave the study at any time for any reason if they wish to do so without any consequences. The investigator can decide to withdraw a subject from the study for urgent medical reasons.

7.5 Replacement of individual subjects after withdrawal

A total of twelve patients is required in this pilot study. When a patient withdraws another patient will be recruited.

7.6 Follow-up of subjects withdrawn from treatment

This is not applicable in this study.

7.7 Premature termination of the study

This is not applicable in this study.

8. SAFETY REPORTING

8.1 Section 10 WMO event

In accordance to section 10, subsection 1, of the WMO, the investigator will inform the subjects and the reviewing accredited METC if anything occurs, on the basis of which it appears that the disadvantages of participation may be significantly greater than was foreseen in the research proposal. The study will be suspended pending further review by the accredited METC, except insofar as suspension would jeopardise the subjects' health. The investigator will take care that all subjects are kept informed.

8.2 Adverse and serious adverse events

Adverse events are defined as any undesirable experience occurring to a subject during the study, whether or not considered related to [the investigational product / the diagnostic procedure]. All adverse events reported spontaneously by the subject or observed by the investigator or his staff will be recorded.

A serious adverse event is any untoward medical occurrence or effect that at any dose:

- results in death;
- is life threatening (at the time of the event);
- requires hospitalisation or prolongation of existing inpatients' hospitalisation;
- results in persistent or significant disability or incapacity;
- is a congenital anomaly or birth defect;
- is a new event of the trial likely to affect the safety of the subjects, such as an unexpected outcome of an adverse reaction, lack of efficacy of an IMP used for the treatment of a life threatening disease, major safety finding from a newly completed animal study, etc.

All SAEs will be reported through the web portal *ToetsingOnline* to the accredited METC that approved the protocol, within 15 days after the sponsor has first knowledge of the serious adverse reactions.

SAEs that result in death or are life threatening should be reported expedited. The expedited reporting will occur not later than 7 days after the responsible investigator has first knowledge of the adverse reaction. This is for a preliminary report with another 8 days for completion of the report.

Due to the nature of the present investigation, no procedure-related adverse events or SAEs are expected to occur, but IFI itself or the underlying disease may cause severe complications.

8.2.1 Suspected unexpected serious adverse reactions (SUSAR)

This is not applicable in this study.

8.2.2 Annual safety report

This is not applicable in this study.

8.3 Follow-up of adverse events

All adverse events will be followed until they have abated, or until a stable situation has been reached. Depending on the event, follow-up may require additional tests or medical procedures as indicated, and/or referral to the general physician or a medical specialist.

8.4 Data Safety Monitoring Board (DSMB)

This is not applicable in this study.

9. STATISTICAL ANALYSIS

Statistical analysis is not necessary in this pilot study. The lesions found on the FDG-PET-CT will be described in the report and compared to other diagnostic techniques. The FDG-PET-CT scan will be evaluated qualitatively (by visual evaluation of the uptake) and quantitatively (by calculating the SUVmax). The calculated SUVmax will be compared to the results of the galactomannan-tests. The aim of this study is to see if FDG-PET-CT is able to localize the IFI and if pathognomic signs for IFIs can be found.

We expect positive signs on the FDG-PET scan in all patients with probable fungal infections. Of the six patients with possible infections we expect at least 2 or 3 to have positive signs on FDG-PET scan. If we can find additional information (positive lymph nodes, lesions in other part of the body) we can not predict.

When there is added value of the FDG-PET-CT we will arrange a larger patient study for which statistical analysis is necessary. Power calculation is not applicable in this study because the aim of this study is to get data to plan a larger clinical study with the appropriate power calculation. These data will serve to calculate the power analysis for a subsequent clinical study.

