9. STATISTICAL ANALYSIS.....	17
10. ETHICAL CONSIDERATIONS.....	18
10.1 Regulation statement.....	18
10.2 Recruitment and consent.....	18
10.3 Objection by minors or incapacitated subjects (if applicable).....	18
10.4 Benefits and risks assessment, group relatedness.....	18
10.5 Compensation for injury.....	18
10.6 Incentives (if applicable).....	19
11. ADMINISTRATIVE ASPECTS AND PUBLICATION.....	20
11.1 Handling and storage of data and documents.....	20

11.2	Amendments	20
11.3	Annual progress report	20
11.4	End of study report	21
11.5	Public disclosure and publication policy	21
12.	REFERENCES	22

SUMMARY

Rationale: Invasive fungal infections (IFIs) can be life threatening, especially in prolonged neutropenic patients. The overall mortality in this group has decreased from 60-80% in the past to 30-40% today because of better diagnostics and antifungals. It is essential to diagnose IFIs and start the right treatment as soon as possible to increase survival rates of the patients. Nowadays, HR-CT as imaging technique and galactomannan (GM)-test (Elisa) in blood and fluid (obtained by broncho-alveolar lavage) are together considered the “gold standard” for diagnosing IFIs, but both techniques have their limitations and provide probable diagnosis at best. It is therefore of invaluable importance to have another non-invasive test which can provide a higher sensitivity and specificity for diagnosing these IFIs. ^{18}F -FDG-PET, and even better the combined PET-CT scan (which correlates anatomic with pathophysiologic imaging) might be this important non-invasive imaging technique with better characteristics to early diagnose IFIs.

Objective: The primary objective of this pilot study is to compare FDG-PET-CT with HR-CT alone and to HR-CT and galactomannan test together for early diagnosing IFIs in neutropenic patients.

Study population: Twelve hematologic patients (age > 18 years with neutropenia and prolonged fever after 72 hours of broad-spectrum antibiotics) will be included in this study. Six of 12 patients will have positive signs (one nodule or more noduli) on the HR-CT for IFI and a positive galactomannan-test, therefore having a probable IFI per definition. Furthermore, six out of 12 patients will have positive signs on HR-CT scan without a positive GM test, therefore having a possible IFI.

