2. OBJECTIVES

Primary Objective:

To evaluate if FDG-PET-CT has added value compared to HR-CT and galactomannan-test, nowadays the silver (or surrogate gold) standard diagnostic techniques for early diagnosing IFIs in neutropenic patients. To evaluate this added value we have the following questions:

- Has FDG-PET-CT additional value as imaging modality compared to the HR-CT thorax? Are their specific imaging characteristics found on FDG-PET-CT in relation to the 3 different described lesions found by HR-CT? Can FDG-PET-CT also provide information about the extension of the known lesions, i.e. is the halo sign on HR-CT involved in the infectious process or is it a sign of decreased perfusion due to infarction?
- Can FDG-PET-CT detect enlarged and/or positive lymph nodes and what is the meaning of these lymph nodes in relation to prognosis or GM detection?
- Is FDG-PET-CT able to find additional infectious lesions that are not visible on HR-CT of the thorax? Can FDG-PET-CT detect smaller lesions than HR-CT by its metabolic positivity and is there a relation between the total amount of metabolic positivity of lesions (mean SUV times area of positivity) and galactomannan positivity, which is a parameter of activity and/or invasiveness of aspergillosis?
- Is FDG-PET-CT able to find additional infectious lesions that are not visible on HR-CT of the thorax because they are found outside the thorax? Sometimes IFI are found in the sinussen or gut or brain or combinations of these localisations.

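### SUVmax is set against galactomannan without lesion size, so if nodules are small and differ in size by galactomannan status, size alone could produce a relation that HR-CT already shows

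*Protocol*

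**What the plan says.** Section 3 has the scan "evaluated qualitatively and quantitatively by calculation of the maximal Standardized Uptake Value (SUVmax"). Section 7.3 asks the reader of the scan to look at "the extension of the lesions found compared to the HR-CT lesions and to the intensity of the uptake of FDG by calculating the SUVmax", and then to compare the quantitative results with the galactomannan (GM) tests. Section 9 repeats SUVmax as the quantitative reading and adds: "The calculated SUVmax will be compared to the results of the galactomannan-tests".

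Section 2 goes further in two ways. It brings small lesions into scope: "Can FDG-PET-CT detect smaller lesions than HR-CT by its metabolic positivity". It also names a second PET quantity and links it to GM: "is there a relation between the total amount of metabolic positivity of lesions (mean SUV times area of positivity) and galactomannan positivity". That second quantity does not reappear in Sections 3, 7.3 or 9.

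On which lesions enter, the Summary speaks of "positive signs (one nodule or more noduli) on the HR-CT for IFI", and Section 4.2 asks for a positive HR-CT suspect for IFI. Neither gives a minimum size. No section mentions lesion diameter, partial-volume loss, scanner resolution or image reconstruction.

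**The concern.** Section 7.3 treats SUVmax as a measure of uptake intensity. For a lesion not much wider than the scanner's resolution, SUVmax depends on size as well as on true uptake, because signal spills out of the lesion into its surroundings. If GM-positive patients tend to have larger nodules, size would push SUVmax up in the same patients whose GM is positive, even with identical uptake per unit of tissue.

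This bears on the primary objective, which is added value over HR-CT and GM. Nodule size can already be read from the HR-CT. A SUVmax-GM relation that diameter explains is not something PET has added. A descriptive report carries the same confounding as a formal test would, and Section 9 says that the pilot's data will be used to plan a larger study and its power calculation. The same blurring matters for the small-lesion question in Section 2: a low SUVmax in a small nodule may reflect its size rather than low metabolic activity.

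**Working it through.** The protocol gives no figure to reproduce: no lesion sizes, resolution, SUV values, test or power. The check asks how large a size effect could be. Every input below except the group sizes is an assumption.

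**Inputs.** Groups of 6 GM-positive and 6 GM-negative patients (Sections 3, 4.1 and 4.2). Assumed: uniform spherical lesion, Gaussian resolution of 5 to 7 mm FWHM, no image noise, no breathing motion, true SUV 5, background 0.5.

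**Step 1: recovery at the lesion centre.** With R = diameter/2 and s = FWHM/2.355,

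RC = erf(R/(√2·s)) − √(2/π)·(R/s)·exp(−R²/(2s²)).

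Example: 8 mm lesion, FWHM 6 mm. s = 2.548 and R/s = 1.570. The first term is about 0.884 and the second about 0.365, so RC ≈ 0.52.

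**Step 2: measured SUVmax** = 0.5 + (5 − 0.5)·RC. For the example: 0.5 + 4.5 × 0.518 = 2.83.

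| Diameter | RC at FWHM 5 / 6 / 7 mm | Measured SUVmax at FWHM 5 / 6 / 7 mm |
|---|---|---|
| 5 mm | 0.29 / 0.19 / 0.13 | 1.81 / 1.35 / 1.08 |
| 8 mm | 0.69 / 0.52 / 0.39 | 3.58 / 2.83 / 2.24 |
| 10 mm | 0.86 / 0.72 / 0.58 | 4.39 / 3.75 / 3.12 |
| 15 mm | 0.99 / 0.97 / 0.90 | 4.97 / 4.85 / 4.57 |
| 20 mm | 1.00 / 1.00 / 0.99 | 5.00 / 4.99 / 4.95 |

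With identical true uptake, a 20 mm lesion reads 5.00/3.58 = 1.4 to 4.95/2.24 = 2.2 times as high as an 8 mm lesion. From about 15 mm upward the effect is small.

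**Step 3: what this does to 6 against 6.** Simulation with 4,000 runs, one lesion per patient and the same true-SUV distribution in both groups (median 5, log-SD 0.4). Only median diameter differs between groups (log-SD 0.3). The two-sided 0.05 exact Mann-Whitney test is a yardstick only; the protocol plans no test.

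| Median diameter, GM+ v GM− | Ratio of median SUVmax (FWHM 5 to 7 mm) | Runs with p < 0.05 |
|---|---|---|
| 10 v 10 mm | 1.00 | 4% |
| 15 v 10 mm | 1.18 to 1.43 | 7 to 19% |
| 15 v 8 mm | 1.43 to 1.93 | 20 to 48% |
| 30 v 20 mm | 1.01 to 1.05 | 4 to 5% |

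Size produces an apparent relation when lesions are small and differ in size by GM status. It does not when sizes are equal or when lesions in both groups are large.

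**Step 4: would the Section 2 measure help?** Mean SUV times area has size as a factor. It rises with lesion extent even when uptake is constant, so it cannot show whether intensity adds anything to size.

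**The case against.** A reader might infer that SUVmax is the protocol's only quantitative PET measure. It is not: Section 2 names mean SUV times area and relates it to GM. What is accurate is that Sections 3, 7.3 and 9 carry SUVmax alone.

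A reader might also infer that the comparison is biased towards a positive result. The documents do not support that. Both conditions are needed, small nodules and a size difference by GM status, and the protocol gives neither. Section 1 offers reasons for a negative GM that need not involve size: fungi other than Aspergillus, a serum sensitivity of 42%, and lavage fluid that does not reach peripheral lesions. These weaken the assumed link between size and GM without excluding it.

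Nor can small nodules be called uninterpretable. In the model an 8 mm nodule reads 2.2 to 3.6 against a background of 0.5, so it would still be visible. What is unsafe is reading its low value as low activity.

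Other objections have some force. Section 2 treats GM as a marker of activity and/or invasiveness, so a relation between disease burden and GM is partly what the protocol is looking for. Section 7.3 already compares lesion extension with HR-CT, and Section 11.1 includes HR-CT results in the data. The plan is descriptive and no decision rule rests on SUVmax against GM. A more detailed analysis plan or imaging manual may also exist. What remains is that Section 9 itself fixes the comparison without size, and the extension reading is not linked to it. If burden drives the relation, HR-CT diameter may show it as well as PET does, and that is the added-value question.

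**Conclusion.** The point holds in conditional form. Sections 3, 7.3 and 9 use SUVmax as the quantitative measure, and Sections 7.3 and 9 compare it with GM without accounting for lesion size. The measure in Section 2 cannot separate size from intensity. Assuming 5 to 7 mm FWHM, nodules below roughly 15 mm and a size difference by GM status, partial-volume loss alone could give a ratio of median SUVmax of about 1.2 to 1.9 in the small-lesion scenarios above. With lesions of 20 mm and more it would be negligible. The consequence is limited to how the pilot is read and what it passes to a larger study: PET could be credited with information already visible on HR-CT. No formal test is invalidated, because none is planned.

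**What to change.** In Section 7.3, record the HR-CT diameter of each lesion from the scans already made. In Section 9, report SUVmax together with diameter for every lesion, and show diameter against GM beside SUVmax against GM for all twelve patients. State that a low SUVmax in a small nodule will not be read as absence of metabolic activity.

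Do not restrict the main comparison by a size cut-off. With six patients per group, a cut-off could empty the GM-negative group if its nodules are the smaller ones, and it would set aside the small lesions that Section 2 asks about.

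While editing, reconcile Section 2 with Sections 3, 7.3 and 9 on whether mean SUV times area will be measured.

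The cost is one extra data column, a few sentences of protocol text, and a more cautious reading of any SUVmax-GM relation. No extra scan or patient is needed.
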